5. SPECIFIC ANALYSIS PROCEDURES

5.1 Planned Sequence of Analysis

Step 1: Planned descriptive analysis of baseline characteristics and systematic evaluation of missing data.

Step 2: Protocolized verification of statistical assumptions for each variable according to prespecified methods.

Step 3: Planned analysis of primary variable (ABC Vineland-3):

- Repeated measures ANOVA according to protocol specifications.
- Post-hoc comparisons conditioned to significant F.
- Preset calculation of effect sizes.

Step 4: Scheduled analysis of quantitative secondary variables (Vineland-3 domains, FOS):

- Repeated measures ANOVA for each variable according to protocol.
- Post-hoc comparisons with prespecified Bonferroni correction.

Step 5: Planned ordinal secondary variable (GAS) analysis:

- Friedman's test for each objective according to design.
- Dunn's post-hoc comparisons according to protocol.

Step 6: Preset sensitivity analysis for missing data based on specified methods.

Step 7: Planned synthesis of findings and interpretation according to pre-established criteria.

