1.2 Secondary Objectives

1. To compare scores by domains of the Vineland-3 (Communication, Daily Life, Socialization) between the three time points.
2. Evaluate changes in GAS (Goal Attainment Scaling) scores for individualized goals.
3. To analyze changes in FOS (Family Outcome Survey) scores for family competencies.
4. Determine skill maintenance between week 15 and week 17 (non-intervention period).

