4.2 Inferential Analysis

4.2.1 Primary Variable Analysis

Main method: One-factor (time) repeated measures ANOVA with three levels.

- **Intrasubject factor:** Time (3 levels: week 0, 15, 17).
- **Dependent variable:** ABC Vineland-3 score.
- **Null hypothesis:** $H_0: \mu_0 = \mu_{15} = \mu_{17}$ (there are no differences between moments).
- **Alternative hypothesis:** H_1 : At least one mean differs.

Post-hoc comparisons: Bonferroni's method for multiple comparisons:

- Week 0 vs. Week 15.
- Week 0 vs. Week 17.
- Week 15 vs. Week 17.

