4.2.2 Analysis of Secondary Variables

Quantitative variables (Vineland-3 Domains, FOS):

- Repeated measures ANOVA (procedure identical to primary variable).
- Bonferroni correction for multiple comparisons.
- Analysis of planned contrasts (linear and quadratic).

Ordinal variables (GAS):

- Friedman's test for repeated measures ($k = 3$ moments).
- Dunn's post-hoc comparisons with Bonferroni's correction.
- Analysis by individual objective (Objective 1, 2, and 3).

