4.5 Significance Criteria and Adjustments for Multiple Comparisons

4.5.1 Level of Significance:

- **Primary analysis:** $\alpha = 0.05$ (bilateral).
- **Confidence intervals:** 95%.

4.5.2 Adjustments for Multiple Comparisons:

- **Within each variable:** Bonferroni correction for post-hoc comparisons.
- **Among secondary variables:** No adjustment (exploratory analysis).
- **Number of comparisons by ANOVA:** 3 post-hoc comparisons.

Bonferroni adjustment formula: $\alpha_{\text{ajustado}} = \alpha / \text{number of comparisons} = 0.05 / 3 = 0.0167$.

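### The F gate on the pairwise comparisons is explicit for the ABC and ambiguous for the Vineland-3 domains; it adds no needed error control and can block the week 15 vs week 17 test

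*Combined protocol and SAP*

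**What the plan says.** The rule for the pairwise comparisons appears in five places in the SAP.

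- **4.2.1 (ABC):** "Post-hoc comparisons: Bonferroni's method for multiple comparisons", followed by the three pairs. No condition on F is written.
- **4.5.2:** three comparisons per ANOVA, each at 0.05/3 = 0.0167. No condition on F is written.
- **5.1 Step 3 (ABC):** "Post-hoc comparisons conditioned to significant F".
- **5.1 Step 4 (domains and FOS):** "Post-hoc comparisons with prespecified Bonferroni correction". No condition on F is written.
- **4.2.2 (domains and FOS):** "Repeated measures ANOVA (procedure identical to primary variable", with Bonferroni as a separate bullet, and a third bullet: "Analysis of planned contrasts (linear and quadratic".

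SAP 1.2 item 4 sets the objective that depends on one of these pairs: "Determine skill maintenance between week 15 and week 17 (non-intervention period". SAP 4.5.2 and 10.3 treat the secondary results as exploratory.

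**The concern.** If F is not significant for a domain, the SAP does not settle whether the pairs are tested. An analyst who takes 4.2.2 to carry the Step 3 condition across would stop. One who follows Step 4 as written would go on. The two could then report different maintenance results for the same domain.

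For the ABC the gate is clear, but its purpose is not. Bonferroni already protects the three comparisons. The omnibus F pools the variability of all three pairs, and two visits two weeks apart may well agree more closely with each other than either does with baseline. In that case the week 15 vs week 17 difference is more precise than the F gives it credit for, and a modest gain followed by a loss can fail the F while the pair itself would pass.

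**Working it through.** **The plan's own figure.** 0.05/3 = 0.016667, which rounds to the stated 0.0167. The SAP gives no power or sample-size calculation to reproduce.

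**Inputs from the documents.** n = 24 (SAP 2.2); norm SD 15 (SAP 3.1, 3.2.1); test-retest reliability 0.64 to 0.92 (protocol 8.1); two-sided 0.05 and three comparisons (SAP 4.5).

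**Assumptions.** The documents give no between-visit correlation, sample SD or expected mean profile. The base case takes correlation 0.8 between week 0 and each later visit, 0.92 between weeks 15 and 17 (the top of the reliability range), and SD 15. Each paired t test uses its own error term, which the SAP does not specify.

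**Why the gate can cost power.** The variance of a within-child difference is 2 × SD² × (1 − r).

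- Week 15 vs 17: 2 × 225 × 0.08 = 36, SD 6.0, standard error 6.0/√24 = 1.22.
- Week 0 vs 15 and week 0 vs 17: 2 × 225 × 0.20 = 90 each, SD 9.49, standard error 1.94.
- Average over the three pairs, which is what the F uses: (90 + 90 + 36)/3 = 72, SD 8.49, standard error 1.73.

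For a 3-point loss the pair's own noncentrality is 3/1.22 = 2.45. The critical t at 0.0167 with 23 df is 2.58, so power without the gate is 46%.

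**Simulation.** 40,000 trials per scenario; F at 0.05 with Greenhouse-Geisser correction; pairs at 0.05/3. Entries are power for the week 15 vs week 17 difference (a 3-point loss in every row).

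| Correlation with baseline / weeks 15-17 | Means at weeks 0, 15, 17 | No gate | Gate |
|---|---|---|---|
| 0.8 / 0.92 | 0, 3, 0 | 46% | 25% |
| 0.8 / 0.92 | 0, 4, 1 | 46% | 30% |
| 0.8 / 0.92 | 0, 5, 2 | 46% | 36% |
| 0.8 / 0.92 | 0, 8, 5 | 46% | 46% |
| 0.64 / 0.92 | 0, 3, 0 | 46% | 11% |
| 0.64 / 0.64 | 0, 3, 0 | 9.5% | 8.4% |

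Separate runs differ by about one percentage point, so the base case is quoted as 25% to 37%.

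**Other settings.**
- All correlations 0.80, a gain of 4 points then a loss of 4: 32.6% without the gate, 31.5% with it.
- A gain of 15 points then a loss of 4: no difference under any correlation tried.
- A pooled error term for the pairs: the gate suppressed a significant loss in at most 2.8% of trials in any scenario.
- Week 0 vs week 17: essentially unchanged by the gate (for example 51% either way at 0, 8, 5 in the base case).

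**Error control.** With all means equal, the chance of any false pairwise finding is about 4.1% to 4.6% without the gate and 2.5% to 3.4% with it.

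**The case against.** **The gate is written once, for the ABC.** Step 4 covers the domains and has none. In 4.2.2 the word identical sits on the ANOVA bullet, and its nearest referent is 4.2.1, which has no gate either. This stands. A reader might infer that the SAP contradicts itself, or that it gates the domains; the text supports neither. The other sections are silent, not opposed, and the gate reaches the domains only on one reading of 4.2.2.

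**A loss would not go unseen.** A reader might infer that the gate hides a loss altogether. It does not: means with 95% intervals and time profiles are planned (4.1.1), and the domain contrasts carry no F condition. In the base case with equally spaced coding, the quadratic contrast at 0.05 has power of 60%, 73% and 84% for the first three profiles in the table. This largely stands, but neither output tests the pair named in the objective. An interval for a visit mean is not an interval for within-child change. The equally spaced quadratic contrast (1, −2, 1) also responds to a gain that is simply held: means 0, g, g give −g. Spaced by actual week it is (2, −17, 15), which is closer to the pair but still mixes in the gain from baseline.

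**The size depends on chosen correlations.** This stands. The 0.64/0.92 case takes both ends of one reliability range and is an extreme. Under equal correlations the cost is about one point of power.

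**A gate before Bonferroni is valid and conservative.** True, and the primary week 0 vs week 17 comparison hardly changes. Dropping the gate is justified by its lack of benefit, not by any invalidity. Even without it, power for a 3-point loss is only 46%.

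**Conclusion.** The point holds as a minor one. The gate is explicit for the ABC and ambiguous for the domains. It adds no needed protection, because Bonferroni alone keeps familywise error at about 4.1% to 4.6%. It can prevent the only planned test of the week 15 vs week 17 difference in the ABC and domain scores.

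The loss of power, from about 46% to 25-37% for a 3-point loss, requires both a small gain (3 to 5 points) and a week 15-17 correlation well above the correlation with baseline. It also rests on n = 24, SD 15 and separate error terms. The documents neither confirm nor exclude these conditions. The primary comparison is not threatened, and the affected result is secondary and exploratory, which keeps the severity low.

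**What to change.** In SAP 5.1 Step 3, replace "Post-hoc comparisons conditioned to significant F" with: run regardless of the omnibus F, at the Bonferroni level of 0.0167. State the same rule in Step 4 and in 4.2.2 for the domains; FOS falls under the same two sections and can share the sentence. Add that the within-child week 15 vs week 17 difference is always reported with its confidence interval for the ABC and each domain. Step 5 is likewise silent on whether Dunn's comparisons require a significant Friedman test, and one clause there would settle it.

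The cost is one sentence repeated, with no new data or staff. Because it alters the primary analysis text, SAP 8.2 would call for the principal investigator's approval and an amendment, so it is best done before analysis. The statistical price is a rise in familywise error under the null from about 2.5-3.4% to 4.1-4.6%, still under the stated 5%.

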2.2 Secondary Objectives

1. Implement the syllabus protocol and MS programs in participating families
2. Apply protocols in children between 3-7 years of age with associated ASD and DND
3. Evaluate agreed goals using Goal Attainment Scaling (GAS) at three time points
4. Identify domains and subdomains of acquired adaptive behaviors
5. To analyze results of the Family Outcome Survey (FOS) in significant caregivers
6. Perform comprehensive statistical analysis of the results obtained

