8.2 Goal Attainment Scaling (GAS)

Description: A method of personalized scales that allow quantifying progress towards specific collaboratively defined objectives.

Modified measuring system: 5-point scale adapted for EA and DND:

- -2 = current performance levels (baseline).
- -1 = progress.
- 0 = expected level of results.
- +1 = somewhat more than expected.
- +2 = much more than expected.

Conversion: Kiresuk-Sherman formula for standardized T-scores (M=50, SD=10).

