9. STUDY PROCEDURES

9.1 Sampling Periods

Phase 1 - PRE-TEST (Baseline - Week 0):

- Control period during therapeutic admission.
- Vineland-3 administration, FOS to significant parents/caregivers.
- Elaboration of collaborative GAS objectives (parents-professionals).
- Complete interdisciplinary diagnostic evaluation.

Phase 2 - INTERVENTION (Weeks 1-14):

- Implementation of the Sentido's® Model according to the syllabus protocol.
- 4 weekly sessions of 60 minutes.
- Daily record of progress by professionals.
- Inclusion of caregivers (12 structured sessions), gradual fading of their participation in the sessions.

Phase 3 - POST-TEST (Week 15):

- Re-administration of Vineland-3, FOS, GAS evaluation after 14 weeks of intervention.
- Skills maintenance evaluation.

Phase 4 - FOLLOW-UP (Week 17):

- Third administration Vineland-3.
- Evaluation of GAS (parent-professional) objectives after two weeks without intervention.
- Post-intervention sustainability analysis.
- Return to usual intervention.

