3.2.2 Goal Attainment Scaling (GAS)

- **Objectives 1, 2 and 3:** Individually defined by family and therapists.
- **Scale:** 5-point ordinal (-2 to +2).
- **Conversion:** T-scores using the Kiresuk-Sherman formula (mean = 50, SD = 10).

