4.6 Calculation of Effect Sizes

4.6.1 For Repeated Measures ANOVA:

- **Partial eta square (η^2):** To assess magnitude of effect
 - Small: $\eta^2 = 0.01$
 - Median: $\eta^2 = 0.06$
 - Large: $\eta^2 = 0.14$

4.6.2 For post-hoc comparisons:

- **Cohen's d:** For differences between pairs of means
 - Small: $d = 0.20$
 - Median: $d = 0.50$
 - Large: $d = 0.80$

Formula: $d = (\mu_1 - \mu_2) / \text{spooled}$

4.6.3 For non-parametric tests:

- **r effect:** $r = Z/\sqrt{N}$ for Friedman test
 - Small: $r = 0.10$
 - Median: $r = 0.30$
 - Large: $r = 0.50$

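### The Goal Attainment Scaling (GAS) omnibus test compares follow-up with a baseline fixed at the bottom of the scale, so a few one-level upward ratings can make it significant

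*Combined protocol and SAP*

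**What the plan says.** - **Scale.** SAP 3.2.2 gives the scale as "5-point ordinal (-2 to +2" (closing bracket omitted). In Protocol 8.2 the entry for the lowest level reads, after its minus sign, "2 = current performance levels (baseline". The next level up, -1, is called progress, and 0 is the expected result.
- **Timing.** Protocol 2.2 sets the objective: "Evaluate agreed goals using Goal Attainment Scaling (GAS) at three time points". At week 0, Protocol 9.1 lists only "Elaboration of collaborative GAS objectives (parents-professionals" and describes no separate baseline rating.
- **Test.** SAP 4.2.2 specifies "Friedman's test for repeated measures ($k = 3$ moments", then Dunn comparisons with Bonferroni correction, and "Analysis by individual objective (Objective 1, 2, and 3". SAP 5.1, Step 5 repeats this: "Friedman's test for each objective according to design".
- **Effect size.** SAP 4.6.3 gives r = Z/√N "for Friedman test".
- **Interpretation.** SAP 5.2.2 labels level -2 (T below 40) a setback and level -1 (T 40-49) no change.
- **Status.** SAP 4.5.2 and 10.3 treat secondary outcomes as exploratory, without adjustment across them.

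**The concern.** The Friedman null says that the three occasions do not differ. Here one occasion is not observed: week 0 is -2 for every child and goal by definition, and the scale has nothing lower. Change from week 0 can only be zero or positive. Rating error, which would partly cancel around a baseline inside the scale, can then push only one way.

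Parents and professionals write the goals together, and they are the only parties Protocol 9.1 names in connection with GAS. SAP 10.1 acknowledges that there is no control group. A significant omnibus result could therefore reflect mildly generous ratings of a few children, none of whom reached the expected level.

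Two related defects affect how the result would be read. The level labels in Protocol 8.2 and SAP 5.2.2 disagree. The effect size assigned to Friedman's test needs a Z, but the test yields a chi-square.

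**Working it through.** **Inputs.** N = 24 (SAP 2.2); k = 3 occasions (SAP 4.2.2); baseline -2 (Protocol 8.2); three goals per child (SAP 3.2.2). Alpha 0.05 two-sided is stated for the primary analysis (SAP 4.5.1) and is assumed here for GAS. Optimistic-rating rates are assumptions.

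**The plan's own figure.** Bonferroni level 0.05/3 = 0.0167. It reproduces.

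**Omnibus statistic.** Let m children move from -2 to -1 at weeks 15 and 17 while the rest stay at -2. Movers have ranks (1, 2.5, 2.5) and the others (2, 2, 2). The mean ranks are 2 - m/N, 2 + m/(2N) and 2 + m/(2N).

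- Uncorrected statistic: [12N/(k(k+1))] × Σ(mean rank - 2)² = N × 1.5m²/N² = 1.5m²/N.
- Tie correction: 1 - [6m + 24(N - m)]/(24N) = 0.75m/N.
- Corrected chi-square: (1.5m²/N)/(0.75m/N) = 2m on 2 df, so p = exp(-m).
- Exact conditional p when all m movers agree: 3 × (1/3)^m = 3^(1-m).

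| m of 24 | chi-square | asymptotic p | exact p |
|---|---|---|---|
| 2 | 4 | 0.135 | 0.333 |
| 3 | 6 | 0.0498 | 0.111 |
| 4 | 8 | 0.018 | 0.037 |
| 6 | 12 | 0.0025 | 0.0041 |

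Without the tie correction, 10 movers are needed (1.5 × 100/24 = 6.25, p = 0.044). The SAP specifies neither tie handling nor exact versus asymptotic p.

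**Rejection rate per goal**, if each child has probability q of being rated one level too high. The persistent rows are binomial tails, P(at least 3) and P(at least 4) of 24. The independent row sums the multinomial probabilities of a child being raised at neither visit, one visit or both.

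| Assumption | q = 10% | 15% | 25% |
|---|---|---|---|
| Same error at both visits, asymptotic p | 44% | 72% | 96% |
| Same error at both visits, exact p | 21% | 50% | 88% |
| Independent error at each visit, asymptotic p | 17% | 34% | 82% |

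**Is the floor the cause?** Simulation (4,000 trials per setting) with a fixed baseline one level above the floor and 10% error in each direction gave about 5.7% rejection with independent errors and 10% with persistent errors. The corresponding figures at the floor were 17% and 44%.

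**Post-hoc step.** Dunn z without tie correction is (1.5m/24)/√(12/(6 × 24)) = 0.2165m. At m = 11, z = 2.38 and adjusted p = 0.052; at m = 12, z = 2.60 and adjusted p = 0.028. So 12 of 24 movers are needed. At the three rates above, with persistent errors, the chance of that many is below 1%.

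**Level labels.** With equal weights and goal intercorrelation ρ, a child at -1 on all three goals has Kiresuk-Sherman T = 50 - 30/√(3 + 6ρ). This is 32.7 at ρ = 0, 36.3 at ρ = 0.3 and 40.0 at ρ = 1. For any ρ from 0 to below 1, SAP 5.2.2 calls this child a setback, while Protocol 8.2 calls every one of the three ratings progress. A single goal still at baseline has T = 50 - 20 = 30, also a setback.

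**The case against.** The strongest reply is that little rests on this test. GAS is secondary and labelled exploratory, and SAP 10.1 already concedes the lack of a control group and possible effects of time. The planned Dunn-Bonferroni step, without tie correction, does not respond to trivial movement. The three-mover figure is the favourable case: it needs the asymptotic tie-corrected p with 21 of 24 rows fully tied, and the higher rejection rates need errors that persist between visits. All of this stands. It limits the point to the omnibus step and lowers its priority. It does not justify testing against a value fixed by definition, because the exploratory label addresses multiplicity, not that.

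A reader might infer more than the documents support:

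- *That nothing can count for the null.* Unchanged ratings leave it standing. Week 17 can also fall below week 15, and that contrast serves the maintenance objective (SAP 1.2).
- *That the plan is silent on whether children reach the expected level.* The Friedman p-value is, but SAP 4.1.2 plans category frequencies and proportions with 95% CIs, and SAP 5.2.2 interprets results by level.
- *That the floor baseline is beyond dispute.* The labels in SAP 5.2.2 would fit a baseline of -1. The point rests on Protocol 8.2, which is the explicit scale definition.

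**Conclusion.** The point holds for the omnibus Friedman test and should be fixed. As Protocol 8.2 defines the scale, week 0 is a constant at the minimum, and 3 of 24 children moving one level (4 with the exact p) are enough to reject. Under the assumed error rates of 10% to 25%, rejection runs from 17% to 96% across the error patterns and p-value methods examined. Those rates are illustrations, since the documents give no figure for rating error.

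It would be too strong to say that a significant GAS result is close to guaranteed, or that every GAS comparison rejects on trivial movement. The first is not shown at low error rates, and the second is wrong for the uncorrected Dunn step and for week 15 against week 17. The primary Vineland-3 analysis is unaffected. The conflict between Protocol 8.2 and SAP 5.2.2, and the mismatch between r = Z/√N and Friedman's chi-square, stand on the text alone.

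**What to change.** 1. Reconcile the level labels and T cut-offs in Protocol 8.2 and SAP 5.2.2, and state the goal weights and intercorrelation used in the T formula.
2. Drop the test against the fixed week-0 value. Keep week 0 as a descriptive reference, so that GAS is still presented at three time points.
3. Report each child's three-goal composite T, summarised at weeks 15 and 17 with a 95% CI against 50. The SAP defines this score but plans no test or estimate of it.
4. Extend the proportions in SAP 4.1.2 to goals at level 0 or above, with a CI that allows for three goals per child.
5. Test week 15 against week 17 by paired Wilcoxon for the maintenance objective.
6. In SAP 4.6.3, use Kendall's W if Friedman is kept descriptively, and apply r only to pairwise Z statistics.

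Cost: no new data are needed. SAP 8.2 classes changed variable definitions as a major deviation, so the principal investigator's approval and a protocol amendment may be required. The change-from-baseline p-value is lost. Optimism from parents and professionals who set the goals and also take part in rating them remains, and should be stated as a limitation.

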5.2 Clinical Interpretation Criteria

5.2.1 Primary Variable (AUC Vineland-3):

- **Clinically significant change:** ≥ 1.0 SD (≥ 15 points).
- **Moderate change:** 0.5-0.99 SD (7.5-14.9 points).
- **Minimum change:** 0.2-0.49 SD (3-7.4 points).
- **No change:** < 0.2 SD (< 3 points).

5.2.2 GAS Variables:

- **Complete success:** T-score ≥ 60 (level +1 or +2).
- **Partial success:** T-score 50-59 (expected level 0).
- **No change:** T-score 40-49 (level -1).
- **Setback:** T-score < 40 (level -2).

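### SAP 5.2.2 labels GAS level -2 (baseline) a setback and level -1 (progress) no change, which contradicts the scale in protocol 8.2

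*Combined protocol and SAP*

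**What the plan says.** Protocol 8.2 describes a five-point GAS scale modified for this population. After its minus sign, the entry for the lowest level reads "2 = current performance levels (baseline". Level -1 is defined as progress. The middle level is "0 = expected level of results", and +1 and +2 are two grades of doing better than expected.

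SAP 3.2.2 keeps the same range, "Scale: 5-point ordinal (-2 to +2", for three goals per child: "Objectives 1, 2 and 3: Individually defined by family and therapists". It converts the levels to "T-scores using the Kiresuk-Sherman formula (mean = 50, SD = 10".

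SAP 5.2.2 then gives the clinical interpretation. Each verbal label is printed with a T-score band and a level number:

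- T of 60 or more (level +1 or +2) is complete success.
- Level 0: "Partial success: T-score 50-59 (expected level 0".
- Level -1: "No change: T-score 40-49 (level -1".
- Level -2: "Setback: T-score < 40 (level -2".

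Step 7 of the analysis sequence in SAP 5.1 says that findings are interpreted by the pre-established criteria. Neither document redefines the levels or reconciles the two sets of meanings.

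**The concern.** The SAP labels read as if the child started at -1, with room to fall to -2. The protocol starts the child at -2, with nothing below. A goal that has not moved is therefore called a setback, and a goal that has moved up one level is called unchanged.

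What is at stake is the written clinical conclusion on GAS. A reader who sees only the labels would take non-response for regression and modest improvement for no response. A setback category also suggests that regression was an observable outcome, which this scale does not allow.

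Timing matters as well. The correction moves labels in the intervention's favour, so making it after the GAS results are known would look like reclassification.

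**Working it through.** **Inputs.** The level anchors come from protocol 8.2. The range, the number of goals and the T conversion come from SAP 3.2.2. The labels, bands and level numbers come from SAP 5.2.2. The documents give neither goal weights nor an inter-goal correlation (rho). For composites I assume equal weights and vary rho.

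**Step 1: reproduce the SAP's bands.** The Kiresuk-Sherman score is

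T = 50 + 10·Σ(w·x) / √[(1 − rho)·Σw² + rho·(Σw)²].

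For one goal the denominator equals w, so T = 50 + 10x whatever rho is.

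| Level x | T = 50 + 10x | SAP band | Protocol 8.2 meaning | SAP 5.2.2 label | Consistent? |
|---|---|---|---|---|---|
| -2 | 30 | below 40 | at baseline | Setback | No |
| -1 | 40 | 40-49 | progress | No change | No |
| 0 | 50 | 50-59 | expected level | Partial success | Strict, but not contradictory |
| +1 | 60 | 60 or more | somewhat above expectation | Complete success | Yes |
| +2 | 70 | 60 or more | well above expectation | Complete success | Yes |

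For a single goal, bands and level numbers agree in every row. The conversion is not the source of the conflict. The words are.

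**Step 2: can a setback occur?** A setback would be performance below baseline. Baseline is -2 and the scale stops at -2, so no level or single-goal T-score represents one. Every goal placed in that category at weeks 15 or 17 would be a goal scored as unchanged.

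**Step 3: does a three-goal composite rescue the labels?** With equal weights the denominator is √[3(1 − rho) + 9·rho].

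| rho | Denominator | All goals at -2: T = 50 − 60/denominator | All goals at -1: T = 50 − 30/denominator |
|---|---|---|---|
| 0 | √3.0 = 1.732 | 15.4 | 32.7 |
| 0.3 | √4.8 = 2.191 | 22.6 | 36.3 |
| 0.5 | √6.0 = 2.449 | 25.5 | 37.8 |
| 1 | √9.0 = 3.000 | 30.0 | 40.0 |

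A child with progress on all three goals has a composite below 40 at every rho shown except 1, and so falls under *Setback* instead of the band printed for -1. All goals at 0 give T = 50 at any rho. The composite therefore does not rescue the labels, and the printed pairing of bands with levels does not carry over to it.

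**Step 4: where the labels are used.** SAP 4.1.2 describes GAS by category frequencies, medians and quartiles. SAP 4.2.2 tests it by Friedman and Dunn procedures, objective by objective. None of these uses the labels, which enter only at interpretation (SAP 5.1, Step 7).

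**The case against.** The best defence is that little depends on the labels. GAS is a secondary variable (protocol 7.2), and secondary results are declared exploratory (SAP 4.5.2 and 10.3). The inference and descriptive tables use the levels themselves, so p-values, distributions and direction of change remain right. The labels also err downward and so cannot create a false claim of benefit. All of this stands, and it limits the severity. It does not make the two labels true.

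A reader might go further than the documents allow in four ways.

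- *That level 0 is a third contradiction.* SAP 5.2.2 itself calls level 0 the expected level, as the protocol does. Reserving complete success for +1 and +2 is a strict grading that understates a met goal, but it is a choice.
- *That all 24 children would be reported as setbacks at week 0.* This assumes that the labels are applied to baseline scores. No section says so, and 24 is only an estimated sample size.
- *That the GAS analysis as a whole is wrong.* Only the verbal classification is.
- *That children below baseline should be counted separately.* Protocol 9.1 provides a daily progress record, but no rule for scoring decline from it. Such a count would need a new definition and perhaps new data.

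**Conclusion.** The point holds for two of the four labels, those for levels -2 and -1. At weeks 15 and 17, every goal at -2 would be misreported as regressed and every goal at -1 as unchanged when the labels are applied by level or by single-goal T. The number of goals affected cannot be known from the plan.

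The contradiction at these levels needs no assumption beyond the printed text, because SAP 5.2.2 states the level beside each label. Only the composite figures rest on assumptions: equal weights, an illustrative range for rho, and use of a composite at all. The plan does not say whether T is computed per goal or across the three goals.

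Severity is should-fix: the error sits in the interpretation of a secondary, exploratory outcome, and the primary Vineland-3 analysis is untouched.

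**What to change.** Before GAS results are interpreted, revise SAP 5.2.2 to follow the protocol 8.2 anchors:

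- -2: no change from baseline.
- -1: progress, below the expected level.
- 0: expected level reached.
- +1 and +2: more than expected.

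Delete the setback category, and add to the limitations in SAP 10.2 that decline below baseline cannot be scored on this scale. State that the labels apply to each goal's level, or to a T-score from a single goal, and not to a three-goal composite. Replacing the partial-success label at level 0 is optional, though the list above does so.

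The cost is SAP wording only, with no new data and no change to any test. If the relabelling is treated as a modified variable definition, SAP 8.2 calls for the principal investigator's approval and a protocol amendment. A dated record is useful in any case, because the change favours the intervention.

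### The two lower GAS interpretation bands in SAP 5.2.2 contradict the scale in protocol 8.2: baseline is called a setback and progress is called no change

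*Combined protocol and SAP*

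**What the plan says.** Protocol 8.2 describes a five-point GAS modified for this population. Its entry for level −2 reads, after the minus sign, "2 = current performance levels (baseline". Level −1 is progress. The middle level is "0 = expected level of results", and +1 and +2 are results above expectation.

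SAP 3.2.2 lists three objectives per child, "Individually defined by family and therapists". It keeps the scale as "5-point ordinal (-2 to +2" and converts it to "T-scores using the Kiresuk-Sherman formula (mean = 50, SD = 10". It does not redefine any level.

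SAP 5.2.2 then sets the interpretation categories, each tied to a T range and a level:

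- *Complete success*: T of 60 or more, levels +1 and +2.
- *Partial success*: "T-score 50-59 (expected level 0".
- *No change*: "T-score 40-49 (level -1".
- *Setback*: "T-score < 40 (level -2".

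SAP 4.2.2 and SAP 5.1 (Step 5) plan the GAS inference as a Friedman test with Dunn comparisons, one objective at a time. SAP 5.1 (Step 7) bases the final interpretation on pre-set criteria.

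**The concern.** Both sections attach words to the same numbered levels, and for the two lower levels the words disagree. Protocol 8.2 puts the starting point at the bottom of the scale; SAP 5.2.2 treats −1 as the point of no change and −2 as a loss. No other section reconciles them.

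What is at stake is the clinical reading of GAS. An analyst who follows SAP 5.2.2 would report setbacks that are only absence of movement, and absence of movement where there was progress. With 24 children and no control group, a few goals in the wrong category would visibly change the description of this outcome. The direction is unfavourable to the intervention. If the labels are corrected only after the results are known, the correction will therefore look like a change made to improve them.

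**Working it through.** **Step 1. Reproduce the plan's own mapping.** The Kiresuk-Sherman score is

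T = 50 + 10·Σ(w·x) / √[(1 − ρ)·Σw² + ρ·(Σw)²],

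where x is the attained level, w the goal weight and ρ the correlation between goals. For one goal the weight cancels and ρ drops out, so T = 50 + 10x. Levels −2, −1, 0, +1, +2 give T = 30, 40, 50, 60, 70. These fall in the bands that SAP 5.2.2 assigns to those levels. For a single goal the numeric cut-offs are consistent; only the words need checking.

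**Step 2. Set the words side by side.**

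| Level | Single-goal T | Meaning in protocol 8.2 | Label in SAP 5.2.2 | Agree? |
|---|---|---|---|---|
| −2 | 30 | baseline | Setback | No |
| −1 | 40 | progress | No change | No |
| 0 | 50 | expected result | Partial success | Same level, same order |
| +1 | 60 | somewhat above expected | Complete success | Same level, same order |
| +2 | 70 | much above expected | Complete success | Same level, same order |

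The conflict lies in the first two rows. It involves no weight, correlation or other assumption.

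**Step 3. What can *Setback* detect?** The scale runs from −2 to +2 and baseline is −2. A goal that worsens below its starting point has no level to be scored at; the lowest it can receive is −2, the same as a goal that never moved. The label therefore cannot separate deterioration from no change.

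**Step 4. Does the unit matter?** SAP 5.2.2 does not say whether the bands apply to each objective or to a composite of three. Suppose a composite with equal weights; the documents give neither weights nor ρ, so both are assumptions. With w = 1 for three goals the denominator is √[3(1 − ρ) + 9ρ] = √(3 + 6ρ). For all three goals at −1 the sum is −3:

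- ρ = 0: T = 50 − 30/1.732 = 32.7
- ρ = 0.3: T = 50 − 30/2.191 = 36.3
- ρ = 0.5: T = 50 − 30/2.449 = 37.8
- ρ = 1: T = 50 − 30/3 = 40.0

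The denominator is below 3 whenever ρ is below 1, so T is then below 40 and progress on all three goals would be called *Setback*. On a composite, then, the match between levels and T ranges from Step 1 fails.

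A composite also takes values between the integer bands. Goals at +1, +1 and 0 with ρ = 0.3 give T = 50 + 20/2.191 = 59.1, which lies above 59 and below 60 and so in no band as written. Single-goal scores do not have this problem.

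**The case against.** The strongest reply is about scope, and most of it stands. GAS is a secondary variable, and SAP 10.3 treats secondary outcomes as exploratory. The Friedman and Dunn tests work on ordinal levels, and the descriptive plan in SAP 4.1.2 reports frequencies by category, medians and quartiles. None of these is specified through the bands of SAP 5.2.2, which enter only at interpretation.

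A reader might go further than the documents allow in four ways.

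- *That success counts are wrong.* They are not shown to be. The bands starting at 50 and 60 agree with protocol 8.2 in level and order, and relabelling leaves those cut-offs in place.
- *That the T cut-offs are themselves wrong because each child has three goals.* That follows only if the bands are applied to a composite. SAP 4.2.2 and 5.1 analyse GAS by objective, and SAP 5.2.2 ties its bands to individual levels, which fits a single-goal T. The supportable criticism is that the unit is not stated.
- *That every child is a setback at week 0.* SAP 5.2.2 gives no time point, so this assumes that the bands are applied at baseline. A goal still at −2 at week 15 or 17 is sufficient to show the problem.
- *That a yes/no count of children who worsened below baseline could be added by rewording.* The planned scale does not hold that information, so such a count would need additional data capture.

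It could also be argued that *Setback* is meant to catch skills gained by week 15 and lost by week 17. The bands classify the attained level and not a change between visits, so a goal that rose and fell back to −2 gets the same label as one that never moved. This defence does not rescue the label, and it leaves *No change* at level −1 unexplained.

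**Conclusion.** The contradiction is explicit and stands without assumptions: two of the four interpretation categories, covering two of the five levels, carry labels that conflict with the trial's own scale. Every goal that ends at −2 or −1 would be described wrongly. How many of the 72 goals that is (24 children × 3 objectives) cannot be known from the documents.

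The consequence is limited to how a secondary, exploratory outcome is put into words, and the error makes the intervention look worse. It should be corrected before GAS categories are reported. The composite figures in Step 4 are conditional on a composite, equal weights and the stated ρ; they show why the unit must be stated and are not a separate error in the plan.

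**What to change.** In SAP 5.2.2, relabel the bands to follow protocol 8.2:

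- level −2 (single-goal T = 30): no change from baseline
- level −1 (T = 40): progress below the expected level
- level 0 (T = 50): expected level
- levels +1 and +2 (T = 60, 70): more than expected

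Delete *Setback*, and add a sentence that this GAS scale cannot record deterioration below baseline. State that the bands apply to each objective separately, in line with SAP 4.2.2 and 5.1.

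If the investigators want the categories on a three-goal composite instead, they would have to fix in advance the weights, ρ, cut-offs suited to the composite, and continuous boundaries that close the gap between 59 and 60.

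The per-objective correction costs a few lines of SAP text and no new data or re-analysis. Since SAP 8.2 lists changes to variable definitions as major deviations, the change should be dated and documented as an amendment, with a statement of whether any GAS results had been seen when it was made.
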